# Summary of the Protocol

As detailed in the research plan and the protection of human subjects sections this study involves a randomized controlled trial of Fathers for Change compared to Batterer Intervention Program. For further details on the sample and inclusion/exclusion criteria, see the Human Subjects section. The Yale School of Medicine Child Study Center Parent and Family Development Program clinic will serve as the participating site. The clinics will recruit participants, allow for data collection/assessments by study staff and offer space for provision of the study treatments.

# **Roles and Responsibilities**

[name] and the study team will review data integrity and safety during weekly team meetings. The post graduate associate and research interns will review assessment data and bring any concerns to [name] immediately if needed or in the context of weekly study review. Drs. [name] (Fathers for change) and [name] (Batterer Intervention) will also provide weekly supervision to study therapists, where they can report any concerns or safety considerations related to study interventions. Any significant study safety concerns related to participants will result in an immediate phone call to [name] and if needed Drs. [name] and [name]. [name] will not participate in data analysis. [name] or another team member masked to participant treatment group will carry out all statistical analyses related to study intervention comparisons.

In accordance with Federal and Institutional regulations, a Data Safety and Monitoring Board (DSMB) for this study will meet quarterly to review aggregated study outcomes data and adverse events. The DSMB will be composed of three clinical investigators with expertise in working with men/fathers, forensic populations, and IPV victims/child witnesses who are not affiliated with this study. [name] will present these aggregated data on study outcomes and adverse events quarterly in a blinded fashion.

# Trial Safety

Participants would be excluded from further participation in the intervention if any of the following occur:

1) psychosis, 2) a domestic dispute or incident of child maltreatment that results in a full no contact order pertaining to the child, 3) suicidal ideation requiring hospitalization. Overall, subjects will be dropped from the study if they show severe symptom deterioration, which would warrant transfer to another level of intervention.

Mechanisms for trial safety and security have been detailed in the Human Subjects Section of this proposal.

The trial would be stopped if study interventions resulted in increased violence toward co-parents or children.

Yale requires disclosure of any conflict of interest for study personnel. Prior to beginning work on the study, all staff will complete a conflict of interest survey. If a conflict is identified, prior to commencing work on the study a conflict of interest plan will be developed by the Yale Research Compliance Administrator, Conflict of Interest Program to ensure faculty or staff are in no way influencing the findings of the research.

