# Weekly and Monthly Measures During Treatment

The RA will meet with fathers via password protected zoom link or in person to complete logs of IPV, substance use and interactions with their children and monthly assessments of working alliance and treatment motivation via computerized survey at the time of their weekly clinical appointment. If fathers do not show for their appointment RAs will phone him to collect the information or email a secure survey. All data will be entered into a secure web-based REDCap database.

**TimeLine Follow-back-Spousal Violence, Child Maltreatment Risk, & Substance Use (TLFB-SV/SU/CM)** will be used to assess specific types of IPV (physical, sexual, psychological) toward partners on any given day, contact with the target child and child maltreatment risk behaviors (yelling, swearing, spanking, slapping, ignoring, harsh punishment). The TLFB-SV/SU/CM will be administered weekly to assess violence, substance use and CM risk behaviors during treatment. This is a reliable and valid instrument that has been used to assess relationship violence over time and links to substance use.  Participants, *the mother of their youngest child and if different their current female partner* will be asked to report IPV and CM throughout treatment.

**Measures of Treatment Targets:** Fathers will complete items from the Parental Acceptance Rejection Questionnaire, COPES and Unified Protocol Skill Use Scale to assess intervention coping skill use and emotion regulation/RF changes during treatment.

**Measures of Treatment Process:** Fathers will complete the **Working Alliance Inventory**,  **Motivation to Change** (85) on a monthly basis and the **Client Satisfaction Questionnaire** at the end of treatment to document (a) the quality of their relationship with their clinician, (b) their perceived motivation for change, and (c) satisfaction with treatment.

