# 4. How was this estimate derived?

Phase I: Seventy-five fathers, the female co-parent of their youngest child, and their child will participate for a total of up to 225 participants. We intend to include all 75 fathers assigned to study interventions for intent to treat analysis. The planned sample size of 75 participants who will provide data for inclusion in our intention-to-treat analysis should provide sufficient power to detect clinically meaningful differences between and within treatment conditions as specified in our primary aims. A sample of 63 people provides power of 80% to detect a standardized treatment group differences at 18 weeks of d = 0.45. For purposes of power estimates, we assumed d = 0.45 will represent a potentially meaningful clinical difference in both our primary and mechanism outcomes. In a pilot study examining F4C on participant IPV effect size for outcome was d = 0.86. We will enroll 75 participants to accommodate a 16% loss to follow-up.

Using these procedures in prior studies, our rate of successful follow-up has ranged from 70-90%. With 280 participant families randomized and an aim of at least 70% completion, we expect to have 196 cases with complete treatment and follow-up data.

**4. Process of Consent/Assent** (*NOTE: When a study includes minors, parent provide permission [not consent] for the child's participation, and the child provides assent for participation)* 

Describe the setting and conditions under which consent/assent will be obtained, including parental permission or surrogate permission and the steps taken to ensure participants' independent decision-making.

Fathers will complete informed consent either in person or online via Yale's REDcap data system, in line with guidance on obtaining informed consent during the COVID-19 pandemic. Each will agree to have their female co-parent contacted for consent of participation of their shared child.

Mothers will complete informed consent related to their own participation and the participation of children in which they are the primary guardian. This will be completed online via Yale's REDcap system..

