2. What participant information will you be collecting? Describe the identifiers that will be included or associated with the data and/or specimens (e.g., names, addresses, telephone/fax numbers, email addresses, dates (date of birth, admission/discharge dates, etc.), medical record numbers, social security numbers, health plan beneficiary numbers, etc.)

We will collect names, birth dates, criminal records, Department of Children and Families records and contact information (phone numbers, addresses and email addresses) from study participants. If a participant drops out of the research study we will make efforts to retain them in the study for intent to treat analysis. This information will be kept with the signed informed consent in a locked cabinet in the PI's office. It will not be linked to study measures which will be locked in another office space under the participants study ID number.

Other potentially identifying information to be collected:

⊠Audiotapes

⊠Videotapes

□Faces (focus groups, photographs or other way that an individual would be physically recognized)

Potential for identification from the bulk of the information, even if direct identifiers are not collected (deductive disclosure).

3. How will the research data be collected and recorded?

Data will be collected via interview and entered directly into an on-line REDCap data system. REDCap is an on-line, secure data capture. Responses to the PDI will be recorded via audio recorders. They will be downloaded onto a secure password protected servers that only study team members will have access. Digital recordings will be conducted by the therapist and stored on a HIPAA secure server. They will be rated by trained therapy fidelity coders. All data will be stored on a password protected and encrypted HIPAA compliant server at the Yale School of Medicine and entered on a secure REDCap database.

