Collection of records from DCF and criminal records: Fathers will sign a release of information for collection of data from DCF related to his arrests for family violence related incidents and reports of IPV and child maltreatment to DCF. An excel spread sheet will be created that will include the names of study participants and their dates of birth. These will be sent to the contact person at DCF who will search records via a secure data transfer (encrypted and firewall protected using Yale's secure file transfer). The contact person who will be a state employee with approved access to the DCF and state arrest databases will search the names and dates of birth. The state employee will fill in the excel spread sheet with the data requested (number of reports to DCF for IPV and CM over the 26 weeks of treatment and number of IPV or CM related arrests over the 26 weeks of treatment). If an incident appears in both databases this will be noted to prevent double counting of a single incident of IPV multiple times due to reporting to both the police and DCF. The completed dataset will be returned to [name] via the same Yale secure file transfer. DCF will not keep any records of this data once transferred back to [name]. The excel sheet will then be updated by [name] with participant study ID numbers and the names and dates of birth will be deleted from the file. This ID only dataset will be saved for merging with other study data for analysis. This will ensure that arrest and DCF data will not be attached to participant names once it returns to Yale. The data will be stored on a password protected server only assessible by the study team.

4. If identifiers will be associated with the data and/or specimens, describe whether a record or list containing a code (i.e., code number, pseudonyms) will be used, where the list will be stored, who will have access to the list and when it will be destroyed.

The only file that will link the study participants to their study ID number will be an excel file kept on a password protected and encrypted computer in the PI's research lab. Only the PI and study RAs will have access to this file.

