Potential risks to confidentiality: As detailed above, every effort will be made to maintain participant confidentiality. Confidentiality with regards to completed research forms will be maintained via numbered reference system maintained by the PI and Project Director. Participants names will appear only on the consent form, HIPPA authorization form and "key" form in a password protected file only accessible by the PI and project director. Subjects who decline participation in the study or those who wish to withdraw from the study can continue in their treatment at the outpatient facilities as they would if they were not approached to participate in a study. As stated above to further protect against potential risks to confidentiality for this population, a Certificate of Confidentiality will be obtained. Participants will clearly be informed of the limits of this confidentiality, which are in cases of suspected child abuse or neglect, and imminent risk for harm to self or others (particularly intimate partner or child).

Potential risks of Behavioral therapies: For the treatment conditions, frequent monitoring (at least weekly) of the participants' clinical status by therapists and research staff will ensure identification and withdrawal from the study of participants who show significant psychological or symptomatic deterioration. If a participant shows significant symptomatic deterioration such that they are a danger to themselves or others or are in need of crisis intervention, the clinician, RA or project manager working with the participant will contact Drs. [name] or [name] immediately. Both are licensed clinical psychologists with extensive clinical experience with IPV offenders, victims and children who have witnessed violence or experienced maltreatment. Drs. [name], and [name] have over 15 years experience working with men with histories of IPV, victims and children who have experienced violence and maltreatment. [name] is also clinical psychologists with decades of experience with clinical populations. Senior clinical supervision will be available at any time a client is being seen. Drs. [name], [name], or will assess the situation and assist with crisis stabilization, treatment planning, or facilitate inpatient psychiatric hospitalization if indicated. Participants who chose to withdraw or not participate in the study will have access to usual care at the facilities where the study is offered.

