Event attribution may include the following study components: 1) Interventions; 2) Research Assessments; or 3) Study Procedures. On the basis of this review, after [name] excuses herself, the DSMB's outside reviewers will deliberate, and submit a written report to the P.I., the Yale IRB and the Program Officer within 48 hours of these meetings, suggesting any recommendations for protocol modifications, or a recommendation to terminate the trial. While no unblinded interim data analysis is planned, if the DSMB independent reviewers suggest that an unblinded interim analysis is required, we will consult with the program official and the IRB, and a statistical penalty for this interim analysis may be taken if it is decided that the trial can continue. All adverse events graded 3 or higher in severity and attribution will be considered as serious adverse events (SAEs), and will be reported within 48 hours to the Yale IRB HIC, and NIH. Reasons for terminating a subject's participation (e.g. "stopping rules") will include: 1) serious adverse reaction to study intervention Fathers for Change or BIP. Anticipated adverse events include increased negative mood, increased danger to female partner or child, and/or rearrests related to IPV or CM offenses or other non-family violence criminal charges. These will be assessed with rating scales. As these scales are assessed at baseline and during the experimental procedure, we will be able to determine if the event is attributable to the research. Otherwise, routine reporting of adverse events data will be done on a quarterly basis corresponding to the quarterly meetings of this study's DSMB, using the following summary table which includes AE severity and attribution, as well as whether or not such AEs were anticipated (ATP) or unanticipated (UNATP).

4. **Potential Benefits:** Identify any benefits that may be reasonably expected to result from the research, either to the participant(s) or to society at large. (*Payment of participants is not considered a benefit in this context of the risk benefit assessment.*)

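### One section limits the agency-records request to 26 weeks although Table 1 schedules records to 12 months, and removal for deterioration is not separated from ending outcome collection

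*Combined protocol and SAP*

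**What the plan says.** **Records.** Section VI, item 3 (how data are collected) has a state employee fill in the "number of reports to DCF for IPV and CM over the 26 weeks of treatment", plus related arrests over the same 26 weeks. Table 1 marks court and arrest records, and child protective services records, at baseline and in the column for the 6- and 12-month follow-ups. Section VI, item 1 describes the same request to the courts division and the child-protection agency with no time limit. The Treatment Phase section gives 18 weekly sessions. The Background description of F4C gives 26 weeks. The Follow-up section counts 6 and 12 months from the end of the intervention.

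**Removal.** Trial Safety lists three triggers under the words "Participants would be excluded from further participation in the intervention if any of the following occur". Its next sentence reads "Overall, subjects will be dropped from the study if they show severe symptom deterioration, which would warrant transfer to another level of intervention". Section VII, item 2 (behavioural therapies) provides for "withdrawal from the study of participants who show significant psychological or symptomatic deterioration". Reportable Events gives, as a reason for terminating a subject's participation, a "serious adverse reaction to study intervention Fathers for Change or BIP", without saying whether treatment, assessment or both end.

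**Retention.** For Phase I: "We intend to include all 75 fathers assigned to study interventions for intent to treat analysis". Section VI, item 2, not limited to either phase: "If a participant drops out of the research study we will make efforts to retain them in the study for intent to treat analysis". For missed weekly appointments: "If fathers do not show for their appointment RAs will phone him to collect the information or email a secure survey". The Phase II analysis text has no intention-to-treat sentence of its own.

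**The concern.** The records window and the removal wording are separate issues, but both decide whether outcome data exist for follow-up.

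The records instruction is the operational one, because it tells agency staff what to fill in. If it is followed as written, records for the later part of follow-up are not requested for any father, removed or not. The measures section calls the FSI-R the primary outcome measure and says it rates child maltreatment risk from self-report, collateral reports and records. A short window would therefore thin one of its inputs at the follow-up times.

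The removal wording concerns fewer fathers, but they are selected on a state that arises after randomisation and plausibly relates to outcome. If staff take leaving the study to mean that assessments stop, the missing data are informative. If removal then differs by arm, the F4C–BIP contrast can be biased. Coparent reports and agency records depend least on the father staying in the study, so they are the sources most worth keeping.

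**Working it through.** **1. Records window.** Inputs: a 26-week window (Section VI, item 3); treatment of 18 weeks (Treatment Phase) or 26 weeks (Background); follow-ups 6 and 12 months after the intervention (Follow-up). Assumptions: the window starts with treatment; 6 months = 26 weeks; 12 months = 52 weeks.

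| Treatment length | 6-month follow-up | 12-month follow-up | Uncovered to 12 months |
|---|---|---|---|
| 18 weeks | 18 + 26 = week 44 | 18 + 52 = week 70 | 70 − 26 = 44; 44/70 = 63% |
| 26 weeks | 26 + 26 = week 52 | 26 + 52 = week 78 | 78 − 26 = 52; 52/78 = 67% |

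On either treatment length the window closes before the 6-month follow-up.

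**2. Removal wording, side by side.**

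- Trial Safety, listed triggers: the intervention ends.
- Trial Safety, next sentence, and Section VII, item 2: the father leaves the study.
- Reportable Events: participation ends, in what is not said.
- Section VI, item 2: efforts to retain a participant who drops out. Removal by the team is not mentioned.
- Weekly measures: contact after a missed appointment. Removal is not mentioned.

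No passage expressly says that outcomes are still collected after the team removes a father.

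**3. Possible size of bias (illustrative only).** The plan gives no removal rate. Its only Phase II allowance, 280 × 0.70 = 196 families with complete data, does not separate out removals.

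Model: standardised on-treatment state, correlated r with outcome; baseline correlated b with both; fathers above a threshold removed, with no later data; baseline-adjusted contrast among those kept. For removal proportion p, with z = Φ⁻¹(1 − p), the kept fathers' mean state is m(p) = −φ(z)/(1 − p) and its variance is v = 1 + z·m − m². The contrast shifts by [m(p₁) − m(p₂)] × (r − βb), where β is the pooled slope on baseline. Each arm's slope is b[1 + r(v − 1)]/[1 + b²(v − 1)].

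- Equal removal: m(p₁) = m(p₂), so the shift is 0.
- 10% v 5%, b = .5, r = .5: m = −.195 and −.109, v = .712 and .810, arm slopes .461 and .475, pooled β ≈ .468. Shift = .0864 × (.5 − .468 × .5) = .023 SD.

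Shift in SD at 10% v 5% (positive means that the arm losing more fathers looks better):

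| b | r = .3 | r = .5 | r = .7 |
|---|---|---|---|
| 0 | .026 | .043 | .061 |
| .5 | .005 | .023 | .041 |
| .7 | −.019 | .001 | .021 |

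At 2% v 1% with b = .5, the shifts are .001, .006 and .010 SD.

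If instead one threshold applies in both arms, treatment shifts state and outcome alike (true effect .12 to .40 SD) and b = .5, the estimate shrinks as follows at r = .3, .5 and .7:

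- 1–2% of BIP removed (140 × .01 = 1.4 to 140 × .02 = 2.8 fathers): under 1%, 1–2% and 2–4%.
- 5–10% removed (7 to 14 fathers): about 1–1.5%, 4–7% and 7–13%.

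**The case against.** **Records.** A reader might infer that no agency records are planned beyond 26 weeks. The documents do not support that. Table 1 schedules them at both follow-ups, and Section VI, item 1 sets no limit. The conflict lies in one passage, and the uncovered percentages apply only if that passage governs and is counted from treatment start. That is correct, and it limits the point to an inconsistency. The inconsistency still sits in the text that specifies the request.

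**Removal.** A reader might also infer that the protocol requires follow-up to stop for deteriorating fathers. The wording does not establish that. The Trial Safety sentence follows a list about the intervention and ends by speaking of transfer to another level of intervention. The Section VII sentence concerns the treatment conditions. Section VI, item 2 uses the word study loosely, since it aims to retain in the study someone who has dropped out of it, and it may already cover removed fathers. This largely stands. What remains is that the retention text promises only efforts, does not name removal by the team, and sits beside wording that distinguishes the intervention from the study.

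**Size.** The bias figures rest on assumed removal rates and correlations and are mostly small. The sign can reverse when baseline is more strongly correlated with state and outcome (b = .7, r = .3). The planned analysis is multi-wave growth modelling, and weekly reports are collected during treatment, so a single adjusted contrast is only a rough guide. This stands in full: the figures show a possible order of magnitude and do not demonstrate bias.

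**Conclusion.** The point holds in two limited parts.

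The 26-week records request is inconsistent with Table 1, with the unlimited description in Section VI, item 1, and with the 18 weeks in the Treatment Phase section. Followed literally from treatment start, it would miss 63% or 67% of the period to the 12-month follow-up, for every father.

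The removal wording leaves open whether outcome collection ends. On the literal reading it conflicts with the Phase I intention-to-treat statement and with the retention statement in Section VI, item 2, and it would create informative missing data. The size and direction of any bias cannot be derived from the documents. In the illustrative model it is zero with equal removal by arm and likely small at low removal rates. The case for change rests on the contradictions and the low cost of repair, not on a demonstrated bias. It should be fixed, with medium confidence.

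**What to change.** 1. Make the records window in Section VI, item 3 run through the 6- and 12-month follow-ups in Table 1. Reconcile the 18- and 26-week statements of treatment length.
2. Reconcile Trial Safety, Section VII item 2 and Reportable Events with the intention-to-treat and retention statements, so that stopping the intervention is distinct from ending outcome collection.
3. State that outcome collection already scheduled continues after removal unless consent is withdrawn: coparent reports, agency and arrest records, and father assessments where the investigators judge them safe and permitted.
4. State, for Phase II as well as Phase I, that fathers are analysed as randomised.

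The clinical stopping criteria, and decisions about safe contact, stay with the investigators.

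Cost: protocol wording, a longer date range in the records request, and a small extra tracking effort for removed fathers.

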Child Mental Health. Symptom dimensions will be derived from father and mother reports on surveys with established reliability, validity, and developmental sensitivity. For data reduction purposes, continuous latent constructs will be identified via measurement models and secondorder factor models conducted in Mplus using standard fit criteria. If necessary, we will use other methods to reduce these data, e.g., latent constructs formed by principal components analysis. The TSCYC and TSCC includes 8 subscales assessing trauma symptoms and more common childhood symptoms and are used for children aged 3 to 17. For infants and toddlers, we will have parents complete the Brief Infant Toddler Social Emotional Assessment (ITSEA) Stratified Randomization. To increase the likelihood treatment groups are balanced on important variables (i.e., , residence with target child, protective order with coparent, substance use) participants will be assigned to treatment through stratified randomization. Following randomization, fathers will be assigned to either 18 sessions (once per week) of Fathers for Change or18 sessions of Duluth Batterer Intervention delivered in an individual format. We anticipate 140 participants in each treatment group. Research assistants managing the data [name] will be blind to treatment condition assignment during analysis. Participants will be recorded as receiving either "treatment 1", or "treatment 2". The research assistants and [name] will not be aware which treatment protocol "treatment 1" or "treatment 2" correspond to until analyses are complete.

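### The harm-stopping statement depends on what the interventions cause, but the DSMB data are described as aggregated and blinded; a quarterly table by coded arm would make it assessable

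*Combined protocol and SAP*

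**What the plan says.** All the relevant text is in Section VII, item 3 (Data and Safety Monitoring Plan).

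- **Trial Safety** gives the trial-level criterion: "The trial would be stopped if study interventions resulted in increased violence toward co-parents or children". It names no measure, comparison, timing or responsible body.
- **Roles and Responsibilities** says the DSMB "will meet quarterly to review aggregated study outcomes data and adverse events", and that a member of the study team "will present these aggregated data on study outcomes and adverse events quarterly in a blinded fashion".
- **Reportable Events** leaves one route to unblinded data: "While no unblinded interim data analysis is planned, if the DSMB independent reviewers suggest that an unblinded interim analysis is required", then "we will consult with the program official and the IRB, and a statistical penalty for this interim analysis may be taken". After each meeting the outside reviewers report, "suggesting any recommendations for protocol modifications, or a recommendation to terminate the trial".
- **Section IV** (the stratified randomization text and the Analytic Plan) has the arms held under the neutral labels treatment 1 and treatment 2 for data management and analysis. The monitoring plan does not mention these labels.

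**The concern.** The stopping criterion is causal. Both arms receive an active programme, and the men are enrolled because of recent violence, so some incidents are expected in each arm whatever the programmes do. A count of incidents does not show whether a programme added to them; a comparison does, and the monitoring plan describes none.

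If the quarterly figures are pooled, harm confined to one arm is diluted. The DSMB can ask for an unblinded analysis, but on pooled figures it may see nothing that prompts the request. The people exposed to that delay are coparents and children, and the protocol rates the study as greater than minimal risk.

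**Working it through.** The plan states no boundary, alpha or event count for harm, so there is no figure to reproduce. The check has two parts.

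**1. What pooling does to a one-arm excess.** Phase II allocates 140 fathers to each arm (Section IV, item 4). With equal numbers and equal follow-up, the pooled rate ratio is (RR1 + RR2)/2.

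- One arm up by half, the other down by half: (1.5 + 0.5)/2 = 1.0.
- One arm doubled, the other unchanged: (2 + 1)/2 = 1.5.

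As proportions, the pooled value is (p0 + p1)/2, so a one-arm excess is halved. The Background section puts repeat violence among BIP completers at 20-30%. I use that only as an illustrative reference; the 15-point excess, the 70 per arm (half of 140) and the two-sided 0.05 level are my assumptions. With p̄ = (p0 + p1)/2:

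By-arm power = Φ{ [|p1 − p0| − 1.96·√(2p̄(1 − p̄)/n)] / √([p0(1 − p0) + p1(1 − p1)]/n) }

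For 20% against 35% at n = 140: (0.15 − 0.1046)/0.0526 = 0.863, giving 0.81.

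| Arm rates | Pooled | By-arm power, 70 per arm | By-arm power, 140 per arm | Pooled test against an exactly known lower rate, 140 per arm |
|---|---|---|---|---|
| 20% and 35% | 27.5% | 0.51 | 0.81 | 0.86 |
| 25% and 40% | 32.5% | 0.47 | 0.77 | 0.81 |
| 30% and 45% | 37.5% | 0.45 | 0.74 | 0.77 |
| 10% and 40% (±15 points from 25%) | 25% | 0.99 | above 0.99 | pooled rate equals the 25% reference |

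The last column shows that sample size is not the obstacle. Pooled data would do as well if the background rate were known exactly, but the documents give only a 10-point range. Against it, 27.5% lies inside. 32.5% is 2.5 points above, less than one standard error (√(0.325 × 0.675/280) = 2.8 points). 37.5% is 7.5 points above, about 2.6 standard errors, and would stand out. Pooling can therefore hide one-arm harm but does not always do so. These are single-look figures, not a proposed monitoring rule.

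**2. Whether another channel supplies the comparison.**

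- *Event attribution* (Reportable Events) is judged case by case from scales taken at baseline and during treatment. Danger to the partner or child and rearrest are listed as anticipated events.
- *48-hour SAE reports* need grade 3 or higher on both severity and attribution. Severity 3 means hospitalization, so much partner or child violence would fall below it.
- *Weekly supervision* runs separately for F4C and BIP. Each supervisor hears concerns from one arm.
- *The interim-results field for multi-site studies* (item 3.d.ii) holds only the template prompt.

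None of these sets one arm's rate beside the other's.

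**The case against.** The strongest reply is that aggregated and blinded need not mean pooled. Where the plan explains its masking, it means neutral arm labels, and the text just before the DSMB paragraph assigns all treatment comparisons to a masked team member. The DSMB may already be meant to receive summaries by coded arm. That reading is possible and cannot be excluded. But the monitoring plan never links the labels to DSMB reports, and calling the data aggregated points the other way. If coded reports are intended, one sentence settles it.

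A reader might infer that one-arm harm could never be seen, or that the stopping statement is the only safeguard. The documents support neither. The DSMB may request unblinding and recommend termination, events are coded for attribution to the interventions, SAEs go out within 48 hours, and clinical status is monitored at least weekly. Nor should anyone infer that the adverse-event table omits arm: the table is not visible in the text available.

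It is also fair to say that an increase could mean an increase over baseline, which pooled data could show. They could not assign it to an arm. Because men enter after an incident in the past 12 months, violence may fall in both arms, so harm could appear as a smaller fall rather than a rise.

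**Conclusion.** The point stands as a cheap improvement, not as proof that harm would be missed. As written, Trial Safety, Roles and Responsibilities and Reportable Events do not show how the stopping statement would be assessed. If the reports are pooled, a one-arm excess is halved, and it cancels completely when the other arm improves by the same amount. In the illustration, 20% against 35% pools to 27.5%, inside the documents' own background range, while a by-arm comparison at 140 per arm has power of about 0.81.

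The conclusion rests on three assumptions: pooled reporting (the more natural reading, but not stated), equal allocation with similar follow-up, and assumed incident rates. If the reports are already split by coded arm, only the wording needs attention.

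**What to change.** - In Roles and Responsibilities, state that a masked analyst gives the DSMB each quarter, in closed session, a table by treatment 1 and treatment 2. It should show IPV and child-maltreatment risk incidents from the weekly timeline follow-back and adverse events, each with father-weeks at risk. State that the DSMB can hold the code.
- Add arrest and CPS records only as they arrive. Table 1 schedules them at baseline and follow-up, and agency staff must search for them, so quarterly requests would be a real extra burden.
- Reconcile Trial Safety, Roles and Responsibilities and Reportable Events so that the stopping statement names the comparison it refers to and the body that assesses it. The threshold and any clinical rule are for the investigators and the DSMB; none is proposed here.
- Describe the table as a safety report with no efficacy test.

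The cost is protocol or DSMB charter wording and a small amount of quarterly reporting. The labels and weekly data already exist, and the presenter already leaves before the DSMB deliberates. The downside is that the DSMB sees by-arm data closely related to the efficacy outcome. The change should not be described as keeping every investigator blind, since those who supervise therapists work within one arm.
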